8.4.5. RABBIT

This study will be conducted in the RABBIT registry using its data sources. The data undergoes regular internal validation checks both manually and automatically. There is no routine on-site medical chart review. However, in case of uncertainties or if insufficient data quality is suspected, there is the possibility to visit participating centers to validate and verify the reported data.

8.5. Study Size

This is a descriptive study without prespecified hypotheses. The goal is to obtain data on all patients who initiate filgotinib during the observational period and thus the numbers will be dictated by the number of filgotinib patients observed in the participating clinics. For illustrative purposes, by applying the rule-of-3 (Hanley & Lippman-Hand, 1983) and assuming an underlying proportion of [any] contraindication of 1%, implies that contraindication would be detected with a certainty of 95% for a sample size of 300 patients; if the underlying proportion of contraindication is 2%, then a sample of 150 patients would suffice (see [Table 10](#)).

Table 10 Sample Size Requirements to Detect Contraindication with 95% Certainty

Underlying Proportion of Contraindication	Sample Size to Detect Contraindication
1%	300
2%	150
3%	100
4%	75
5%	60

In terms of precision, if the proportion of patients at high risk of MACE, for example, is assumed to be 10% among a sample size of 300 users of filgotinib, then this will be estimated with a precision (standard error) of 1.7% resulting in a 95% confidence interval (CI) of 6.6% to 13.4% (Altman, 1991). Other scenarios of precision are provided in the following table.

Table 11 Standard Error by Study Size and Underlying Proportion

Proportion*	Study Size			
	200	300	400	500
2%	1.0%	0.8%	0.7%	0.6%
5%	1.5%	1.3%	1.1%	1.0%
10%	2.1%	1.7%	1.5%	1.3%
15%	2.5%	2.1%	1.8%	1.6%

* Proportion of patients at high risk of MACE, VTE or serious and opportunistic infection.

8.6. Data Management

The study will be conducted by making use of secondary data collected prospectively by the individual registries. Each registry has its own data management processes.

8.6.1. ARTIS

As previously described, health and demographic information within Sweden is collected in a series of registers with a high degree of completeness resulting from the mandatory and semiautomated registration of their data. Based on each Swedish resident's unique personal identification number, issued to all Swedish residents alive in 1947 or born/immigrated thereafter, linkage of data from different registers is possible. The registers are maintained by

governmental bodies (the main registers used in this study are held by the National Board of Health and Welfare [Socialstyrelsen] and Statistics Sweden [Statistiska centralbyrån]), who may perform data linkages and provide deidentified data for research purposes.

The data warehouses of ARTIS reside on restricted, double backed-up servers at the Clinical Epidemiology Division at the Karolinska University Hospital Campus. ARTIS data are housed at the Clinical Epidemiology Division and linked to the data received from the National Board of Health and Welfare and/or Statistics Sweden using the unique personal identification number that all Swedish residents receive. Trained staff perform this linkage, in addition to data cleaning and analysis. All work with these data warehouses is done by trained staff in adherence with local guidelines on good programming, data management practices, and archiving. Data, programs, and documents related to study reports will be maintained for a minimum of 10 years.

8.6.2. BIOBADASER

Data will be entered in an online application designed ad hoc and will be monitored by a person specifically hired and trained to do this. In addition, these data must be downloaded to a relational database that will allow queries to be performed in order to conduct the analysis.

[figure not shown]

Figure 4 Flowchart Showing the Data Management Process in BIOBADASER

8.6.3. BSRBR-RA

This study is conducted by making secondary use of data collected by BSRBR-RA, which has an established data management process.

The primary aim of the BSRBR-RA is to monitor the long-term safety of drugs used to treat rheumatoid arthritis. Clinical data is captured from NHS sites using a secure and encrypted online database. Appropriate security and governance documentation are in place including System Level Security Policy, Data Management Plan, Information Governance Risk Review, Forced

Transport Layer Security for transfer of data, Stakeholder Responsibilities and organizational standard operating procedures (SOPs) detailing data security and information governance.

8.6.4. DANBIO

Data are collected real-time in a web-based system with user-interfaces for patients and for health professionals, which include edit checks at the time of data entry. Dataset for research purposes will go through data management before delivery.

Via a unique personal identification number that each Danish citizen receives at birth, DANBIO data can be linked to administrative registries run by the government; these are considered to be virtually complete.

8.6.5. RABBIT

After being enrolled (baseline visit), patients and their rheumatologists will complete questionnaires during regular follow-ups, which will take place after 3 and 6 months and afterwards every 6 months. The completed case report forms (CRFs) (physician and patient questionnaires) are sent by fax to the German rheumatic-disease research center (DRFZ). To avoid misrouting, fax numbers are stored electronically in the fax machine.

Forms arriving in the central coordinating office are reviewed daily. Medical data managers are responsible for study monitoring (organization of schedules, coding, dropout research, etc.). AEs and SAEs are recorded following the ICH guidelines (CPMP/ICH/377/95/E2A). AEs and SAEs are registered continuously in a separate AE database. Diagnoses are coded using the MedDRA on the preferred term (PT) level; the coding is updated with every MedDRA update. To analyze the outcomes of interest all relevant PT terms are grouped.

Every month, a new longitudinal dataset is created by adding the new data. Twice a year a final dataset is created, which includes all answers to queries, particularly regarding SAEs and therapies. The calculations presented in the half-yearly reports are based on those datasets. Older versions of final datasets are stored electronically. The original data is kept, backups are made on a weekly basis.

8.7. Data Analysis

Detailed methodology for the analyses of data included in this study will be documented in the statistical analysis plan, which will be created by the investigators from the 5 registries, dated, filed, and archived by the MAH. Data analysis summarized in the protocol may be modified in the statistical analysis plan to reflect usage of the most up-to-date methodology used by the different registries.

Data from this non-interventional study will be summarized using univariate descriptive statistical methods. Categorical variables will be summarized by number and percentage of patients in each categorical definition and include 95% CIs. Counts for missing values will be also tabulated but missing values will not be considered in the percentages. Continuous variables

will be summarized descriptively (mean, standard deviation, and median, lower quartile, upper quartile, minimum, maximum, 95% CIs).

Follow-up

Among women of childbearing potential (aged 18-49 years) who start filgotinib, the number and proportion who become pregnant will be reported. Similarly, the number and proportion of patients who have a diagnosis of TB or who are administered a live attenuated vaccine will be reported. The proportion of patients who have a test for lipids at 12 weeks since initiation of filgotinib will be reported; we will not evaluate the lipid levels.

Should a VTE event occur, subsequent changes to filgotinib use will be reported (persistence or discontinuation).

All statistical analyses will be performed by the registries using SAS (ARTIS, DANBIO, RABBIT) or STATA (BIOBADASER, BSRBR-RA).

Reports

Two study reports are envisaged: an interim report at approximately 33 months after start of data collection (24 months after start of data collection + at least 9 months for running the analyses and drafting the report) and a final report at approximately 60 months after start of data collection (48 months after start of data collection + 12 months for running the analyses and drafting the report). The interim report will comprise the baseline and follow-up results from all patients initiating filgotinib since start of data collection until month 24. The final report will comprise the baseline and follow-up results of all patients initiating filgotinib since start of data collection until month 48.

As the timing of filgotinib reimbursement and implementation of the aRMMs and identification of the first identified filgotinib user will differ across the 5 countries of interest, the individual registry reports will have different timelines. The timelines for the consolidated interim and final report outlined in the paragraph above are triggered by the registry that last identified the first patient using filgotinib after launch/commercial availability for the treatment of RA and implementation of the aRMMs.

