7. RESEARCH QUESTION AND OBJECTIVES

The objectives of this study are as follows:

- To quantify the proportion of users of filgotinib being at high risk (as defined in the RMP) of developing MACE, VTE, or serious and opportunistic infections at baseline
- To quantify the proportion of filgotinib users among the very elderly (≥ 75 years) patients being initiated on filgotinib at the recommended dose of 100 mg once daily
- To quantify the proportion of filgotinib users with moderate to severe renal impairment being initiated on filgotinib at the recommended dose of 100 mg once daily
- To quantify the proportion of users of filgotinib who are being treated for active TB at the time of filgotinib treatment initiation and during follow-up (while continuing filgotinib treatment)
- To quantify the proportion of users of filgotinib who have a history of viral hepatitis at the time of filgotinib treatment initiation and during follow-up (while continuing filgotinib treatment)
- To quantify the proportion of female patients of childbearing potential who are pregnant at the time of filgotinib treatment initiation or become pregnant while continuing filgotinib treatment during follow-up
- To assess the proportion of filgotinib users receiving live, attenuated vaccines at the time of filgotinib initiation or at any time during follow-up while continuing filgotinib treatment
- To assess the proportion of filgotinib users with filgotinib discontinuation following a VTE event
- To describe prescribing physicians' adherence to recommendations for patient screening and laboratory monitoring (if available), specifically:
 - To assess the proportion of filgotinib users with evidence of having performed screening for TB prior to initiation of filgotinib
 - To assess the proportion of filgotinib users with evidence of having performed lipid monitoring 12 weeks after initiation of filgotinib
- To assess the proportion of filgotinib users with evidence of having performed the following laboratory tests prior to initiation of filgotinib: absolute neutrophil count (ANC), absolute lymphocyte count (ALC), hemoglobin (Hb) level

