8.2.6. Index Date, Follow-up, Inclusion and Exclusion Criteria

For all analyses, the index date in each registry will be the date a patient starts filgotinib treatment (i.e. the date of first identification of filgotinib exposure in the registry) on or after launch/commercial availability for the treatment of moderate to severe RA and implementation of the aRMMs in each country. The patient follow-up time is defined as the time from the filgotinib index date until the earliest of treatment discontinuation, study withdrawal (withdrawn from the registry, death or loss to follow-up) or end of study.

The observational (study) period for each registry starts at the index date of the first patient starting filgotinib treatment in the registry (i.e. start of data collection). End of the study period will be at 48 months after the start of data collection in the registry (i.e. end of data collection).

To be included a patient has to be aged 18 years or older at the index date. Further inclusion criteria are specified in the following sections for each registry; patients must meet all eligibility criteria.

There are no restrictions to patient inclusion in terms of either historical data or minimum amount of follow-up. Furthermore, patients can be included if they have previously used filgotinib, in which case the patient will have 2 or more treatment lines and therefore 2 or more index dates.

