- Diagnosis of viral hepatitis: yes/no
 - Date of diagnosis
- Patient is currently pregnant: yes/no
 - Weeks pregnant
- Date of most recent full term pregnancy (for women aged < 50 years old)
- The patient is suffering from a serious and opportunistic infection (as defined by MedDRA): yes/no
 - Infection type
 - Date of diagnosis

Dose and age are already variables for this study and thus the use of 100 mg in patients aged ≥ 75 years old and in patients with chronic kidney disease can be addressed.

- Screening:
 - TB
 - Date of screening
 - Result of screening test

Concomitant Medication

- Concomitant use of other immunosuppressant:
 - Type, name, and dose (where recorded)

Additional Variables: Laboratory and Counselling

BIOBADASER is the only registry that can supplement their data through additional data collection screens based on clinical practice. The additional variables are summarized below.

Table 5 Additional Variables in BIOBADASER

Variable			
ANC (neutrophils)	Value	units	Date
ALC (lymphocytes)	Value	units	Date
Hb	Value	units	Date
HDL	Value	units	Date
LDL	Value	units	Date
Total cholesterol	Value	units	Date
triglycerides	Value	units	Date
HDL:LDL	Value	units	Date
Advice given on contraceptive use	y/n		
Advice given on spermatogenesis	y/n		
Advice given on breast feeding	y/n		

ALC = absolute lymphocyte count; ANC = absolute neutrophil count; Hb = hemoglobin; HDL = high density lipoprotein; LDL = low density lipoprotein

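### The rule dropping missing values from percentages conflicts with the objectives that count recorded evidence of screening and tests, and biases those adherence figures upward if blanks are treated as missing

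*Protocol*

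**What the plan says.** Section 8.7 of the protocol sets one rule for categorical variables: "Counts for missing values will be also tabulated but missing values will not be considered in the percentages". It names no exception.

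Section 7 defines the screening and monitoring objectives by the presence of a record among users. For TB: "To assess the proportion of filgotinib users with evidence of having performed screening for TB prior to initiation of filgotinib". For lipids: "To assess the proportion of filgotinib users with evidence of having performed lipid monitoring 12 weeks after initiation of filgotinib". The objective on neutrophil count, lymphocyte count and haemoglobin before initiation is built the same way.

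On the data, section 8.3.1.2 says: "BIOBADASER is the only registry that can supplement their data through additional data collection screens based on clinical practice". Table 5 in that section lists the blood counts and lipids as value, units and date. Only the three counselling items are yes/no. Table 9 confirms that lipid monitoring is available in BIOBADASER alone. TB screening is listed by date and result in BIOBADASER and BSRBR-RA, and without any field structure in RABBIT. The ARTIS and DANBIO adherence lists contain no screening item.

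For the lipid analysis, section 8.7 says: "The proportion of patients who have a test for lipids at 12 weeks since initiation of filgotinib will be reported". Section 8.2.6 adds: "There are no restrictions to patient inclusion in terms of either historical data or minimum amount of follow-up". It ends follow-up at the earliest of discontinuation, withdrawal or end of study. Section 8.7 puts every initiator up to month 24 in the interim report and every initiator up to month 48 in the final report.

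**The concern.** In most descriptive tables a missing value is an unknown, and leaving it out of the denominator is a defensible convention. An endpoint defined as evidence that a test was done works differently. A patient with no test leaves an empty field, and that empty field is what the study is looking for. Dropping it removes the non-adherent patients from the denominator and leaves mainly those who were tested.

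The error has one direction: it favours adherence. It also falls where blanks are to be expected. The additional BIOBADASER items follow clinical practice, and section 8.4.2 has follow-up data recorded at routine consultations or at least once a year. At stake is whether the reported percentages, and the 95% confidence intervals attached to them, can reveal that recommended tests were not done.

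**Working it through.** **The plan's own figures.** The protocol gives no expected adherence percentage. Its only worked precision for a proportion (section 8.5: 10% among 300 patients) reproduces: √(0.10 × 0.90 / 300) = 1.73%, and 10% ± 1.96 × 1.73% = 6.6% to 13.4%. That calculation uses all users as the denominator.

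**Effect of the missing-value rule.** Let t be the true proportion tested and q the share of untested patients who have an explicit not-done entry. The documents give neither, so both are assumptions shown over a range. With blanks dropped:

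reported proportion = t / [t + (1 − t) × q]

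| True t | q = 0 | q = 5% | q = 20% | q = 50% | q = 100% |
|---|---|---|---|---|---|
| 70% | 100% | 97.9% | 92.1% | 82.4% | 70% |
| 30% | 100% | 89.6% | 68.2% | 46.2% | 30% |

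For example, at t = 70% and q = 5%: 0.70 / (0.70 + 0.30 × 0.05) = 0.70 / 0.715 = 97.9%. At q = 0 the result is 100% whatever t is. Table 5 lists no not-done field for blood counts or lipids, so a literal application there sits at or near q = 0. If every user stays in the denominator and no record counts as no evidence, the reported figure equals t.

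**Consequence for lipids once blanks count as no evidence.** All initiators up to the cut are then in the denominator, including those who started too late to reach week 12. Twelve weeks is 84 / 30.4375 = 2.76 months. With T months of accrual:

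- Uniform uptake, share = 2.76 / T: 11.5% at T = 24 and 5.7% at T = 48.
- Linearly rising uptake, share = 1 − (1 − 2.76 / T)²: 21.7% at T = 24 and 11.2% at T = 48.

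Section 8.1 expects uptake to be greater in the latter part of the study; the linear shape is my assumption. With no early discontinuation, a true 90% among patients who reach week 12 would read:

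- month 24: 0.90 × 0.885 = 79.7% (uniform) or 0.90 × 0.783 = 70.5% (rising)
- month 48: 0.90 × 0.943 = 84.8% (uniform) or 0.90 × 0.888 = 79.9% (rising)

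Discontinuation before week 12, for which the documents give no rate, would lower these further. The TB and blood-count endpoints are assessed before initiation, so they need no such restriction.

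**The case against.** The strongest reply is that the objectives already define a yes/no attribute for every user. If each registry derives that indicator for all its filgotinib patients, no record becomes a no, nothing is missing, and the rule never applies. This stands as a possibility, so a reader should not infer that the figures are certain to be wrong or to reach 100% by construction. The protocol does not state the coding, and Table 5 lists variables rather than response options. But each registry runs its own analysis, and as the text stands a registry could follow either section.

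Missing counts are to be tabulated, so the all-user percentage can be rebuilt. That is true of the point estimate: with 210 tested and 90 blank, 210/210 = 100% is printed but 210/300 = 70% is recoverable. The printed percentage and its interval would still rest on the wrong denominator. For lipids, the 90 would also mix untested patients with those who never reached week 12.

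A reader might infer that the lipid figure is both inflated and diluted. It cannot be both. Dropping blanks also drops untested late starters; dilution arises only when all initiators are kept.

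A reader might also treat the absence of a week-12 window as an error in itself. A window and an evaluable set are ordinary matters for the statistical analysis plan, which is not shown. They enter here only because the correction makes them necessary. The missing-value rule is different: it is stated in the protocol and conflicts with the objectives. Section 8.7 does let the analysis plan modify the analysis, but for the purpose of using the registries' most up-to-date methodology.

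Finally, counting every blank as non-adherence mixes poor recording with poor practice. That is fair, and it is why both percentages should be shown.

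**Conclusion.** The concern holds as a conflict between a fixed rule in section 8.7 and the objectives in section 7. If blanks are treated as missing, the affected percentages are biased upward: a true 70% reads as 100% with no not-done entries, 97.9% with 5% and 92.1% with 20%. The direction follows from the formula. The size rests on assumed testing rates and not-done shares.

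The scope is limited. It covers blood counts and lipids in BIOBADASER, and TB screening in BIOBADASER, BSRBR-RA and RABBIT, where the RABBIT coding is not stated. A reader might infer that the study's whole measure of physician adherence fails. The documents do not support that. Starting dose in older or renally impaired patients, contraindicated use, live vaccines and discontinuation after VTE are separate endpoints and do not depend on whether a test was recorded. Section 7 also marks the screening and monitoring objective as subject to availability. Within that objective, though, these registries supply all the data there are.

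**What to change.** In section 8.7, exempt the evidence-of-testing endpoints from the missing-value rule. Use as denominator all eligible initiators in registries that collect the item, count no record as no evidence, and show the missing-excluded percentage as a secondary line.

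For lipids, limit the denominator to patients still on filgotinib and under observation through a stated window around week 12, and report the number non-evaluable.

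The cost is about two sentences in section 8.7 and one extra table column, with no new data collection. The downside is that blanks caused by poor recording count as non-adherence. The leading figure is then a lower bound on true testing and should be labelled as such. The change should be made before the interim analysis, where the late-starter share is largest.

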6.2. Physician Adherence

Physician adherence implies compliance with the SmPC and the HCP Guide. Firstly, this includes the avoidance of administering filgotinib to contraindicated patients: those with active TB, or active serious infection or being pregnant at initiation of treatment and while continuing filgotinib treatment. Secondly, the physician should undertake appropriate screening prior to prescribing filgotinib: screening for TB and viral hepatitis. Furthermore, information on the use of live, attenuated vaccines during, or immediately prior to, filgotinib treatment, and the provision of guidance to women of childbearing potential will be evaluated. Lastly, prescribed doses should be in line with the recommendations. Thus, this will be evaluated for patients aged

≥ 75 or patients with moderate to severe renal impairment whose starting dose should be 100 mg daily.

In terms of adherence during filgotinib use, several endpoints should be monitored:

- Given that pregnancy is a contraindication for filgotinib, should a woman become pregnant, filgotinib must be discontinued.
- If a VTE occurs (“clinical features of DVT/PE”), filgotinib should be discontinued and the patients be evaluated.
- Patients should be monitored for the development of signs and symptoms of TB.
- Lipid parameters should be monitored at 12 weeks after initiation of treatment.
- Live attenuated vaccines should be avoided during filgotinib treatment.

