8.3.2. Variables to be Collected During Patient Follow-up

The variables to be collected during the follow-up which will describe endpoints (see Section 6.2) related to aRMMs adherence are provided in the following table. These therefore include pregnancy, use of vaccines and lipid monitoring. Monitoring of TB following the initial screening for latent disease is not included: firstly, testing is not required and; secondly, evaluating whether clinicians routinely check for signs and symptoms is not be feasible via registry data.

As well as the occurrence of the variables, appropriate dates will be collected. Furthermore, the patients' index dates, end of treatment and end of follow-up dates will be used to estimate the exposure time.

Table 9 Availability of Endpoints to Assess Adherence by Registry During Patient Follow-up

Follow-up Variable	ARTIS	BIOBADASER	BSRBR-RA	DANBIO	RABBIT
Pregnancy	Yes	Yes	Yes	Yes	Yes
Dx of incident TB	Yes	Yes	Yes	Yes	Yes
Viral hepatitis	Yes	Yes	Yes	Yes (only history)	Yes
Administration of live attenuated vaccine	No	Yes	Yes (HZ only)	No	Yes
Lipid monitoring (approx.. 12 weeks after initiation of filgotinib)	No	Yes	No	No	No

Dx = diagnosis, HZ = herpes zoster, TB = tuberculosis

In addition to the above variables, the occurrence of a VTE event whilst the patient is using filgotinib will be identified and specifically the subsequent treatment pattern occurring such as discontinuation of filgotinib will be recorded.

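### Stopping filgotinib after a pregnancy is a stated adherence endpoint that no specified output reports, and for TB the follow-up analysis counts diagnoses, not TB treatment with filgotinib continued

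*Protocol*

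**What the plan says.** All references are to the Protocol.

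- **Section 6.2, general rule.** Physician adherence includes not giving filgotinib to contraindicated patients: "those with active TB, or active serious infection or being pregnant at initiation of treatment and while continuing filgotinib treatment".
- **Section 6.2, endpoints during use.** For pregnancy: "Given that pregnancy is a contraindication for filgotinib, should a woman become pregnant, filgotinib must be discontinued". VTE also carries a discontinuation item. The TB item is only monitoring for signs and symptoms.
- **Section 7.** The pregnancy objective counts women of childbearing potential who are pregnant at initiation or become so on treatment. The TB objective counts users "who are being treated for active TB at the time of filgotinib treatment initiation and during follow-up (while continuing filgotinib treatment"). One objective concerns discontinuation after an event, and it is for VTE.
- **Section 8.3.2.** The follow-up variables are said to describe the 6.2 adherence endpoints. Table 9 lists pregnancy and diagnosis of incident TB. The text below the table provides for recording the later treatment pattern after VTE only. On timing: "As well as the occurrence of the variables, appropriate dates will be collected". End-of-treatment dates are also used, with exposure time as their stated purpose.
- **Section 8.7, Follow-up.** Pregnancy: "Among women of childbearing potential (aged 18-49 years) who start filgotinib, the number and proportion who become pregnant will be reported". TB: "Similarly, the number and proportion of patients who have a diagnosis of TB or who are administered a live attenuated vaccine will be reported". VTE: "Should a VTE event occur, subsequent changes to filgotinib use will be reported (persistence or discontinuation").

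**The concern.** The study is there to judge whether the risk minimisation measures work, largely by describing what prescribers do. Two events in the same 6.2 list, pregnancy and VTE, carry the same kind of prescriber action. Only VTE is given an objective, a recorded variable and a reported result for that action. The pregnancy endpoint is stated in 6.2 and then has no counterpart in the later sections.

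If the plan is followed as written, the reports will give how many women became pregnant but not how many of them stayed on a drug that the protocol contraindicates in pregnancy. For TB, the objective separates patients who continue filgotinib from those who do not, and the reported quantity removes that separation.

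**Working it through.** The protocol gives no figure for this point, so the main check sets the sections side by side.

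| Event | 6.2 during-use item | Section 7 objective | Post-event filgotinib status in 8.3.2 | 8.7 output |
|---|---|---|---|---|
| VTE | Discontinue and evaluate | Discontinuation after VTE | Recorded | Persistence or discontinuation |
| Pregnancy | Discontinue | Pregnant at start or on treatment | Not mentioned | Occurrence only |
| TB | Monitor signs and symptoms | Treated for active TB while continuing filgotinib | Not mentioned | TB diagnosis only |

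**Pregnancy.** Reading across, 8.7 agrees with the follow-up part of the Section 7 objective. The break lies between 6.2 and everything after it: 8.3.2 says its variables describe the 6.2 endpoints, but the discontinuation endpoint has no variable or output.

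**TB.** Treatment for TB follows its diagnosis. A patient diagnosed on filgotinib and stopped the same day counts in 8.7 but need not meet the Section 7 objective. A patient treated for TB with filgotinib continued counts in both. The 8.7 figure therefore cannot be split into the two groups, and Table 9 lists no TB-treatment variable that would do it.

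**What the pregnancy figure can show (assumed numbers).** Take 100 women aged 18-49, 3 pregnancies on drug, and filgotinib stopped in k of the 3.

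- 8.7 output: 3/100 = 3.0% for k = 0, 1, 2 or 3.
- Compliance with the 6.2 criterion: k/3 = 0%, 33%, 67% or 100%.

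This is true by construction. It shows that the output carries no information on the criterion; it does not measure the size of an error.

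**How many events to expect (assumed shares).** Section 8.5 uses 300 users as an illustrative study size. Assume 20-30% are women aged 18-49 and 2-5% of those become pregnant on drug; neither range is in the protocol.

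- Women: 300 × 0.20 = 60 to 300 × 0.30 = 90.
- Pregnancies: 60 × 0.02 = 1.2 to 90 × 0.05 = 4.5, so about 1 to 5 over all registries.
- Even if all of 3 pregnancies led to discontinuation, the exact 95% lower limit would be 0.025^(1/3) = 0.29, giving an interval of 29% to 100%. Individual listings are more useful here than a percentage.

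**Whether the data allow it.** Event dates and end-of-treatment dates are planned (8.3.2). BSRBR-RA collects continuation, dates and reasons for stopping (8.4.3), BIOBADASER records treatment changes and discontinuation (8.4.2), and RABBIT has pregnancy-specific forms (8.8.5).

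**The case against.** The case against has several parts.

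- **The pregnancy analysis already matches its objective.** This stands. A reader might infer that the 8.7 proportion fails to measure the stated pregnancy objective. It does not fail; the mismatch is with the 6.2 endpoint.
- **Section 6.2 has no stop-on-TB item.** This also stands. A reader might treat TB as parallel to pregnancy, but the during-use list names only monitoring, and 8.3.2 explains why that is not evaluated. The TB point is confined to the difference between the Section 7 objective and the 8.7 output.
- **Occurrence is informative in itself.** Correct. Section 6.1 refers to encouraging contraception, and 6.2 says guidance to women of childbearing potential will be evaluated. Pregnancies on drug bear on that and should still be reported.
- **No false verdict on the measures follows.** A reader might infer that the study could declare the measures a failure although prescribers complied. Section 8.5 calls the study descriptive without prespecified hypotheses, and no success threshold is set, so that consequence is speculative.
- **The SAP may supply it.** Section 8.7 leaves detailed methods to the SAP and allows modification, and the SAP is not shown. But the gap also lies in the objectives and the specified follow-up recording, and the protocol does state a post-event readout where it wants one, for VTE.
- **Dating is weak.** This stands as a limit on the remedy. The ARTIS baseline list defines current pregnancy as more than 25 weeks, and the BSRBR-RA baseline list has yes/no only. Follow-up ends at treatment discontinuation (8.2.6), so a pregnancy recorded after stopping could be missed, which would tilt the observed cases towards women who continued.

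**Conclusion.** The concern holds in a limited form. For pregnancy, a stated during-use adherence endpoint, discontinuation, cannot be read from any output the protocol specifies; compliance anywhere from 0% to 100% would give the same reported figure. For TB, the 8.7 measure is broader than the Section 7 objective and merges patients who stopped with those who continued. The pregnancy limb is the stronger one.

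The conclusion rests on the protocol text alone and not on the assumed event rates, which serve only to show that counts will be very small. The point merits correction because the endpoint is already stated and the remedy is cheap. It does not invalidate the planned occurrence proportions.

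**What to change.** 1. **Section 8.7:** keep the pregnancy and TB occurrence proportions. Add, for each on-treatment pregnancy and each on-treatment active TB diagnosis, the number with filgotinib discontinued versus continued afterwards, derived from the event date and the end-of-treatment date. Present this as a patient-level listing or a small table per registry.
2. **Time to stop:** report the interval from recorded event date to end of treatment only where a registry's dating permits.
3. **Section 8.3.2:** extend the sentence on treatment pattern after VTE to pregnancy and active TB.
4. **Section 7 (and the abstract):** add a pregnancy item on discontinuation, parallel to the VTE objective. The TB objective already refers to continuing filgotinib and needs no rewording.
5. **Section 8.9:** state that counts will be very small, that pregnancy is dated differently across registries (ARTIS in particular) so the interval may not reflect when the prescriber knew, and that pregnancies recorded after treatment ended may be missed.

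Cost: wording in these sections and one small listing per registry. It uses dates already planned for collection and measures only what the protocol itself states.
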